11.2 Sample Size/Accrual Rate

No formal statistical hypothesis testing is planned for the primary analysis of the Phase I portion of the study. In the Phase II portion of the study, 51 participants will be enrolled to estimate the 2-year progression free survival. Sample size calculation is based on providing an estimate of the PFS with a 95% confidence interval $\pm 10\%$ under the hypothesis that 2-year PFS is 85%.

If there are no DLTs in the Phase 1 portion of the study, and if 100% of the Phase 1 participants are treated identically to those in the Phase 2, data from the Phase 1 and 2 portions can be combined to complete the phase 2 portion of the study.

The primary endpoint of the phase II portion will be to estimate the two-year progressionfree survival for AVD-brentuximab vedotin which will be done using Kaplan-Meier estimates and corresponding 95% confidence intervals based on standard errors using Greenwood's formula.

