After cycle 2 and post-therapy, progression-free survival will be estimated for participants whose FDG-PET findings were negative and those whose findings were positive using Kaplan-Meier estimates and corresponding 95% confidence intervals based on standard errors using Greenwood's formula. Positive predictive value after 2 cycles and post-therapy will be estimated as the proportion of PET-positive participants who progress or die before two years; negative predictive value after 2 cycles and post-therapy will be estimated as the proportion of PET-negative participants who are progression-free and alive at two years. Sensitivity of FDG-PET at cycle 2 and post-therapy will be estimated as the proportion of participants who progressed or died prior to year 2 whose FDG-PET was positive. Specificity of FDG-PET at cycle 2 and post-therapy will be estimated as the proportion of participants who are alive and progress-free at 2 years whose FDG-PET was positive. Exact two-sided 95% confidence intervals will be used for all estimates.

Log-rank analysis will be used to evaluate HAART status at baseline for difference in outcome in terms of overall survival and progression free survival. The frequency and proportion of different histologic subtypes will be calculated.

The frequency of neurotoxicity in participants taking AVD and brentuximab vedotin in combination with/without HAART will be tabulated. A binomial test of proportions will be used to test the difference in additional toxicity between those participants taking AVD

and brentuximab vedotin on HAART vs. those participants not on HAART.

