die before two years; negative predictive value after 2 cycles and post-therapy will be estimated as the proportion of PET-negative patients who are progression-free and alive at two years. Sensitivity of FDG-PET at cycle 2 and post-therapy will be estimated as the proportion of patients who progressed or died prior to year 2 whose FDG-PET was positive. Specificity of FDG-PET at cycle 2 and post-therapy will be estimated as the proportion of patients who are alive and progress-free at 2 years whose FDG-PET was positive. Exact two-sided 95% confidence intervals will be used for all estimates.

Log-rank analysis will be used to evaluate HAART status at baseline for difference in outcome in terms of overall survival and progression free survival. The frequency and proportion of different histologic subtypes will be calculated.

The frequency of neurotoxicity in patients taking AVD and brentuximab vedotin in combination with/without HAART will be tabulated. A binomial test of proportions will be used to test the difference in additional toxicity between those patients taking AVD and brentuximab vedotin on HAART vs. those patients not on HAART.

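### PET specificity is defined as the proportion of event-free participants with a positive scan, which is 1 minus specificity

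*Combined protocol and SAP*

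**What the plan says.** Section 11.4 of the AMC protocol sets out four accuracy measures for FDG-PET after cycle 2 and post-therapy:

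- PPV: the "proportion of PET-positive participants who progress or die before two years".
- NPV: the "proportion of PET-negative participants who are progression-free and alive at two years".
- Sensitivity: the "proportion of participants who progressed or died prior to year 2 whose FDG-PET was positive".
- Specificity: "estimated as the proportion of participants who are alive and progress-free at 2 years whose FDG-PET was positive".

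The paragraph closes with "Exact two-sided 95% confidence intervals will be used for all estimates".

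Section 16.4 of the LYSARC protocol repeats the specificity definition for the French participants: the "proportion of patients who are alive and progress-free at 2 years whose FDG-PET was positive". Section 16.0 of that protocol says that the AMC Statistical Center will analyse the French and US data pooled, so this is one analysis described in two places. No other section of either document corrects the wording.

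**The concern.** Specificity is the proportion of people without the condition whose test is negative. The plan takes the right denominator, participants alive and progression-free at two years, but counts the positive scans among them. That is the false-positive rate. The three neighbouring definitions are correct, so only this estimator is inverted.

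The prognostic value of PET for two-year PFS is a stated secondary objective (1.2.4). Section 2.4.6 notes that PET is often positive in HIV without malignancy, and sections 8.2.3 and 8.3.3 warn that false positives may be more common in this population. Section 2.6 presents validation of the cycle-2 scan in HIV as an important goal. Specificity is the measure that speaks most directly to the false-positive question. If the definition is programmed as written, a highly specific scan is reported as non-specific, and the reverse.

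**Working it through.** **1. Fix the 2×2 table.** The PPV, NPV and sensitivity definitions in 11.4 determine it: the test is positive when PET is positive, and the condition is progression or death within two years.

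| | Progressed or died by 2 years | Alive and progression-free at 2 years |
|---|---|---|
| PET positive | TP | FP |
| PET negative | FN | TN |

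**2. Translate each definition.**

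- PPV as written = TP/(TP + FP): correct.
- NPV as written = TN/(TN + FN): correct.
- Sensitivity as written = TP/(TP + FN): correct.
- Specificity as written = FP/(FP + TN). The standard form is TN/(FP + TN), so written = 1 − specificity.

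The error in the reported value is written − true = (FP − TN)/(FP + TN) = 1 − 2 × specificity. It is largest when the scan performs best, and it vanishes only at a specificity of 50%. The written quantity also moves the wrong way: each added false positive raises it.

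**3. Illustrate the size.** The documents give no value for specificity or for the false-positive rate, so there is no plan figure to reproduce. Two inputs come from section 11.2: 51 participants and an assumed two-year PFS of 85%. They agree with the ±10-point precision stated there: 1.96 × √(0.85 × 0.15/51) = 0.098.

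Expected event-free participants: 0.85 × 51 = 43.35, taken as 43. This assumes that every event-free participant has a PET result and known two-year status. The false-positive counts below are assumptions, shown over a range. Intervals are Clopper-Pearson, taken as the meaning of exact in 11.4.

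| Assumed FP of 43 | True specificity (95% CI) | Reported as written (95% CI) | Error, percentage points |
|---|---|---|---|
| 2 | 95.3% (84.2 to 99.4) | 4.7% (0.6 to 15.8) | (2 − 41)/43 = −90.7 |
| 4 | 90.7% (77.9 to 97.4) | 9.3% (2.6 to 22.1) | (4 − 39)/43 = −81.4 |
| 9 | 79.1% (64.0 to 90.0) | 20.9% (10.0 to 36.0) | (9 − 34)/43 = −58.1 |
| 13 | 69.8% (53.9 to 82.8) | 30.2% (17.2 to 46.1) | (13 − 30)/43 = −39.5 |
| 22 | 48.8% (33.3 to 64.5) | 51.2% (35.5 to 66.7) | (22 − 21)/43 = +2.3 |

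In each row the two point estimates sum to 100% and the interval limits are mirror images. With no false positives the plan would report 0/43 = 0% where specificity is 43/43 = 100%. In the rows with 2, 4, 9 and 13 false positives, the interval as written does not overlap the correct one.

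**The case against.** The error itself cannot reasonably be disputed; the case on the other side is about how much it matters.

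- The affected analysis is secondary, and 11.4 describes the secondary analyses as descriptive and exploratory. No test or decision rule uses specificity, and removal at cycle 2 for progressive or stable disease rests on CT criteria alone (4.6.8). The log-rank comparison, the Kaplan-Meier curves by PET status, PPV and NPV are free of this error. All of this stands.
- The slip is easy to recognise beside three correct definitions, and a careful programmer would probably compute the right quantity. That is likely, but doing so silently departs from the written plan.
- No information is lost, because the correct value is 1 minus the written one, with mirrored limits. This is true, but only for a reader who notices.
- The denominator of 43 may be too high. Participants who stop therapy early are followed for survival only (8.4.1), and the post-therapy scan is timed from Cycle 6 Day 15 (8.3.3), so some may lack a scan or two-year progression status. This affects the illustration, not the algebra.

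**Conclusion.** The concern holds. As defined in AMC section 11.4 and LYSARC section 16.4, the quantity labelled specificity is 1 minus specificity, at both scan times. This follows from the definitions alone and needs no assumption about the data.

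The size depends on the true specificity: the reported value is off by 1 − 2 × specificity. With 43 event-free participants and assumed false-positive counts of 4 to 13, true values of 90.7% to 69.8% would be reported as 9.3% to 30.2%. Those counts are assumptions, and complete PET and two-year follow-up data are taken for granted.

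The consequence is confined to one estimator of a secondary, exploratory objective, and arises only if the text is followed literally. The primary two-year PFS estimate and the sample size of 51 are untouched. The definition is nevertheless wrong as written and should be corrected before the analysis is programmed.

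**What to change.** In the specificity sentence of AMC section 11.4 and of LYSARC section 16.4, replace the final word *positive* with *negative*. Specificity then becomes TN/(TN + FP), the PET-negative fraction of those alive and progression-free at two years, consistent with the other three measures. The planned exact intervals can stay as they are.

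The cost is one word in each of two documents. No new data, assumption, sample-size change or design change is needed.

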2.4.3 Considerations regarding brentuximab vedotin, CD30, and HIV

CD30 has also been studied in HIV replication, in addition to lymphoma. In fact, increased levels of the soluble form of CD30, sCD30, are predictors of progression to AIDS⁴⁴⁻⁴⁷. Levels of sCD30 also have been shown to correlate with HIV viremia levels and clinical outcome in patients with primary HIV infection in the pre-HAART era⁴⁷. Furthermore, CD30 stimulation directly induces HIV expression through activation of the transcription factor NF-kB⁴⁵⁻⁴⁷. In addition, CD30/CD30L interactions lead to virus production also in primary CD4+ T cells from HIV-positive patients⁴⁷. Both agonistic anti-CD30 antibodies and CD30L-expressing, glutaraldehyde-fixed CD8+ human T cell clones significantly enhanced HIV expression in human CD4+ T cells obtained from HIV-infected individuals⁴⁴⁻⁴⁷. This data suggests that the activation of CD30 expression in HIV-infected CD4+ T cells may allow the interaction of these cells with CD30L-expressing cells and, therefore, favor HIV replication⁴⁴⁻⁴⁷. The result of the use of the brentuximab vedotin and its effects on HIV replication will be monitored closely in this study. All participants on study must be on concurrent HAART therapy. We will test for

a multiplexed inflammatory marker panel that includes sCD30, as well as several other molecules (several soluble cytokine receptors and BAFF/BLyS and CXCL13 (BLC/BCA-1) for changes with the use of brentuximab vedotin and correlate this with changes in HIV viral load as well as clinical outcome. See Section 2.6 for a description of all correlative studies.

2.4.4 Considerations regarding progressive multifocal leukoencephalopathy associated with HIV, brentuximab vedotin, and HIV-cHL

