- 3.1.16 Participants are required to be on antiretroviral regimens that are in accordance with the current International AIDS Society guidelines concurrently with chemotherapy. The specific agents are at the discretion of the Investigator and the use of investigational agents currently available on an expanded access basis is allowed. Use of experimental antiretroviral agents or those containing zidovudine (including Combivir and Trizivir) or ritonavir (includes Norvir[®] or Kaletra[®]), Cobicistat, Didanosine (Videx[®] or Videx EC[®]), or similar potent CYP3 inhibitors are

prohibited, as explained in Section 2.4.5. In order to be eligible, participants taking zidovudine or ritonavir, Cobicistat, Didanosine, or other CYP3 inhibitors must change to a different regimen 7 days prior to therapy initiation. Changes to HAART therapy during the study may be made if medically necessary (toxicity, failure of regimen, etc.). Participants must be on HAART for at least 7 days prior to therapy.

- 3.1.17 Negative for Hepatitis B, or if infected with Hepatitis B, receiving anti-Hepatitis B therapy. All participants will be required to be screened for Hepatitis B. Per IDSA and AASD guidelines, those participants that show no immunity, defined by the lack of Hepatitis B surface antibody, and show evidence of chronic infection (i.e., HBsAg+, HBcore+, HBsAB-) will be required to be on anti-Hepatitis B therapy during the study in order to be eligible. Patients will be permitted to enroll in the study provided normal liver function tests (see Section 3.1.9) and no evidence of cirrhosis. The exact Hepatitis B therapy will be at the discretion of the infection disease specialist or investigator. However, all patients who present with acute hepatitis B or show normal transaminases and are HBsAg+ and IgM+ for Hepatitis core antigen will not be eligible for trial enrollment.
- 3.1.18 Patients diagnosed with Hepatitis C who are Hepatitis C antibody positive, whether Hepatitis C RNA level is measurable or not, must have no evidence of cirrhosis and have liver function tests that conform to Section 3.1.9.
- 3.1.19 Brentuximab vedotin is partially metabolized via the CYP3A4 pathway and is cleared from the cells via the P-glycoprotein pump. Therefore, participants must discontinue use of the following agents within 7 days prior to therapy as per Appendix XIII.
 - Strong CYP 3A4 inhibitors that treat HIV, see 3.1.16.
 - Other strong CYP3A inhibitors.

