4.4.2 HAART

HAART is a requirement for the duration of the study. Participants must be on HAART therapy for at least 7 days before therapy. The specific agents are at the discretion of the Investigator and use of agents currently available on an expanded access basis is allowed. Use of experimental antiretroviral agents or those containing zidovudine (including Combivir® and Trizivir®), ritonavir (including Kaletra®), Cobicistat (Stribild®), or another potent CYP3 inhibitor are prohibited. In order to be eligible, participants taking zidovudine- or ritonavir-based HAART must change to a different regimen 7 days prior to therapy initiation. Changes to HAART therapy may be made if medically necessary (toxicity, failure of regimen, etc.).

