11.4 Analysis of Secondary Endpoints

Descriptive summaries and exploratory analyses for secondary objectives will be conducted. Significance for comparisons will be at the p<0.05 level.

Secondary objectives include:

1. To evaluate toxicity of AVD and brentuximab vedotin with HAART.

- 2. To estimate the partial response rate, complete response rate, overall survival (OS), event free survival at 2 and 5 years. To evaluate effect of AVD and brentuximab vedotin on CD4 and CD8 counts after 2 cycles, 6 cycles, and every 3 months after treatment completion for one year.
- 3. To evaluate effect of AVD and brentuximab vedotin on viral load after 2 cycles, 6 cycles, and every 3 months after treatment completion for one year
- 4. To investigate the prognostic value of FDG-PET scans at baseline and after 2 cycles in participant with HIV and HL with respect to 2 year progression free survival.
- 5. To evaluate HAART status at baseline for difference in outcome.
- 6. The characterization of histologic subtypes in HIV-HL in the HAART era.
- 7. To assess additional neurotoxicity in combination with HAART and AVD and brentuximab vedotin.

The frequency of AEs and their severity will be tabulated to evaluate tolerance of AVD and brentuximab vedotin with HAART. Further, binomial probabilities and their 95% confidence intervals will be used to estimate the response rates (i.e., partial response rate, complete response rate, overall response rate) and event free survival at 2 and 5 years of AVD and brentuximab vedotin for a treatment of participants with stage III/IV HIV-associated Hodgkin Lymphoma.

Repeated measures analysis of variance (ANOVA) models will be used to evaluate the effect of AVD and brentuximab vedotin on CD4 counts, CD8 counts and viral load after 1, 4, and 6 cycles, and every 3 months after treatment completion for one year.

Log-rank analysis will be used to investigate the prognostic value of FDG-PET scans at baseline, after 2 cycles and post-therapy in participants with HIV and HL with respect to progression free survival.

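### The neurotoxicity test compares participants on and off HAART, but HAART is mandatory for everyone, so the off-HAART group is empty by design

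*Combined protocol and SAP*

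**What the plan says.** In AMC section 11.4, item 7 of the secondary list reads: "To assess additional neurotoxicity in combination with HAART and AVD and brentuximab vedotin". The analysis text then says: "The frequency of neurotoxicity in participants taking AVD and brentuximab vedotin in combination with/without HAART will be tabulated". A binomial test of proportions follows, comparing participants taking AVD "and brentuximab vedotin on HAART vs. those participants not on HAART". LYSARC section 16.4 carries the same wording (item 8 of its list), with the test set between patients taking AVD "and brentuximab vedotin on HAART vs. those patients not on HAART". Section 11.4 calls the secondary analyses descriptive and exploratory, and sets p<0.05 for comparisons.

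On HAART itself:

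- AMC section 2.4.3: "All participants on study must be on concurrent HAART therapy".
- AMC section 3.1.16: "Participants must be on HAART for at least 7 days prior to therapy".
- AMC section 4.4.2: "HAART is a requirement for the duration of the study".
- LYSARC section 8.1 (item 16) and section 10.3 impose the same entry and on-study rules.
- AMC section 3.0 and LYSARC section 8.0 rule out any waiver of eligibility.

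Sections 3.1.16 and 4.4.2 of the AMC protocol allow the regimen to be changed for medical need and give toxicity as an example. The concomitant-medication rules (AMC 7.3.6, LYSARC 10.9) provide for recording a change or a discontinuation of antiretrovirals.

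**The concern.** A two-group test needs two groups. Under the protocols' own rules every participant belongs to the first group, so the only inferential analysis written for the neurotoxicity objective has no comparator.

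The protocol treats overlapping neuropathy as a real worry: AMC section 2.4.5 restricts the permitted antiretrovirals partly for that reason. Left as written, the plan gives the sponsor two poor choices. It can drop a prespecified test at analysis without explanation. Or it can run the test on whoever happened to stop antiretrovirals and risk reporting a HAART effect that is an artefact of why they stopped.

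**Working it through.** **The plan's own figure.** No sample size, rate or power is given for the HAART comparison. The only relevant figure is the phase II total of 51, justified by the precision of 2-year PFS:

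n = 1.96² × 0.85 × 0.15 / 0.10² = 48.98, rounded up to 49. At n = 51 the half-width is 1.96 × √(0.85 × 0.15 / 51) = 9.8 points. The stated 51 is consistent with this.

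**Group sizes under the protocol rules.** With HAART required at entry and throughout, and no waivers, the groups are n₁ = 51 on HAART and n₀ = 0 off HAART. LYSARC section 16.0 pools the French and US data, and both protocols have the same rule, so neither country can supply the missing group.

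**The test.** The difference in proportions is x₁/n₁ − x₀/n₀, with variance p₁(1 − p₁)/n₁ + p₀(1 − p₀)/n₀. With n₀ = 0 the second proportion is 0/0 and its variance term divides by zero. The statistic is undefined.

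**Could a comparator come from elsewhere?**

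- *External control.* The outside ABVD series in AMC section 10.3 and Appendix XIV is used only for T-cell counts. The neuropathy figures in AMC section 2.4.5 (1% with EBVP plus AZT or DDI, 31% with ABVD plus HAART) are background from regimens without brentuximab vedotin, and section 11.4 does not refer to them.
- *Participants who stop after entry.* No analysis group is defined from the concomitant-medication record. Such a group would be formed after baseline and by the participant's course on treatment. Because toxicity is a listed reason for changing HAART, neuropathy could be why someone is off HAART and not a result of it. More such participants would not remove that confounding.

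**What can be estimated.** A single proportion on HAART, with a Clopper-Pearson 95% interval. The lower limit is the 2.5% quantile of Beta(x, n − x + 1) and the upper limit the 97.5% quantile of Beta(x + 1, n − x). At n = 51:

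| Count | Rate | Exact 95% CI | Why this count |
|---|---|---|---|
| 0/51 | 0% | 0 to 7.0% | Lower extreme |
| 3/51 | 5.9% | 1.2 to 16.2% | Near the 5% grade 3 sensory neuropathy in AMC 2.4.1 |
| 5/51 | 9.8% | 3.3 to 21.4% | Near the 10% in the AMC 4.7 stopping rule |
| 24/51 | 47.1% | 32.9 to 61.5% | Near the 48% any-grade rate in AMC 2.4.2 |

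The widest half-width over all counts is 14.3 points. The counts are illustrations: the 5% and 48% come from studies outside this population.

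**The case against.** The strongest case against acting is about weight. These analyses are labelled exploratory, a test with an empty arm will visibly fail, and the harmful version (a confounded test on people who stopped HAART) depends on an unknown number of them. The objective in AMC section 1.2.7 concerns the neurotoxicity of the combination; the word *additional* appears only in the statistical sections. Section 11.4 already tabulates adverse events by severity, so much of the objective survives. All of this is fair, and it limits the damage. It does not supply the missing group, and a prespecified test that either cannot run or is biased when it can should not stay in the plan.

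Some narrower points stand as limits:

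- The figure of 51 is the phase II maximum. The secondary objectives are headed for both phases and phase I allows up to 18, so the single-arm denominator could reach 51 + 18 = 69, with a widest half-width of about 12.3 points. The comparator stays at zero.
- Only the on-versus-off effect is ruled out. Differences between HAART regimens could still be described, but section 11.4 does not specify that comparison.
- That neuropathy would make someone stop HAART is plausible, not documented. The protocols list toxicity as a reason for change and record discontinuation for any reason.
- The log-rank analysis of baseline HAART status in the same section has a similar weakness if status means on or off. That is a separate point.

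**Conclusion.** The concern holds. The comparator is 0 of 51 by design, the test is undefined, and the additional neurotoxicity from HAART is not estimable. This rests on the HAART rule being followed. If some participants stop antiretrovirals, the test becomes computable but does not estimate a HAART effect.

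This should be fixed, but it is contained: the primary PFS analysis, the stopping rule in AMC section 4.7 and the overall neurotoxicity rate on HAART do not depend on it.

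**What to change.** In both protocols (AMC 11.4, LYSARC 16.4):

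1. Delete the with/without-HAART tabulation and the binomial test.
2. Report the proportion of all treated participants with neurotoxicity by CTCAE grade, with an exact 95% interval. State whether phase I participants are included. State also that routine adverse event reporting covers events attributed to therapy (AMC 6.4, LYSARC 14.4).
3. Add a descriptive summary by cycle of the FACT/GOG-neurotoxicity scores. The last questionnaire is at Cycle 6 Day 1, so it misses neurotoxicity after the last two doses. For participants who complete treatment, the AMC CTCAE record runs to the 6-8 week visit and covers that period; for early discontinuation it runs to one month (AMC 6.4.1).
4. State that a single-arm design with mandatory HAART cannot isolate the contribution of HAART.
5. Remove *additional* from item 7 of the AMC list and item 8 of the LYSARC list.

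The HAART requirement itself is not in question. The cost is a wording amendment, with CTEP and IRB approval (AMC 13.7) and French ethics committee and competent authority approval (LYSARC 19.10). No procedure or data item is added, since the CTCAE grades and questionnaire scores are already collected.
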